## Methods:

This is a 15 or 29-day, randomized, multicenter, multi-dose, open label study. Subjects, who are at least 12 years old and not more than 16.9 years old with moderate to severe plaque psoriasis, will be randomized to treatment with either DFD-01 spray 15-day treatment or DFD-01 spray 29-day treatment in a 1:1 ratio. These investigational products will be applied twice daily to all affected areas on the body excluding face, scalp, groin, axillae and other intertriginous areas. Subjects must have  $\geq 10\%$  body surface area (BSA) treated to achieve maximal use exposure.

Subject visits will take place at Screening, Baseline (Day 1), Day 8, Day 15, Day 29 (as appropriate) and Day 43 or 57 (if needed to confirm recovery). Clinical determinations of disease severity will be conducted using the Investigator Global Assessment (IGA) for overall severity at each visit. Subjects will be tested for HPA axis function using the ACTH stimulation test (a cosyntropin i.v. or i.m. injection) at the Screening Visit (at least 14 days and no more than 28 days prior to Baseline) and at the End of Treatment Visit (i.e., Day 15 for the 15-day treatment arm or Day 29 for the 29-day treatment arm). If HPA axis is suppressed at the End of Treatment Visit, another test will be administered approximately 28 days later (at Day 43 or 57, as appropriate) to confirm recovery. The ACTH stimulation test will be repeated approximately every 28 days until recovery is confirmed (or until the cause of suppression is diagnosed). Pre-stimulation and post-stimulation cortisol levels will be measured in serum and saliva.

At the time of the screening ACTH stimulation test, a PK blood sample will be taken to obtain a baseline value (PK screening sample). At the End of Treatment Visit, subjects will apply the last dose of study product at the clinic up to 60 minutes after a pre-treatment PK blood sample is taken (0 hour – End of Treatment Visit). PK blood samples will then be collected at 1, 3 and 6 hours ( $\pm$  5 minutes) after application of the study product.

Local cutaneous safety evaluations (including atrophy, telangiectasia, pruritus, pain and burning/stinging) will be performed at Visits 2, 3, 4, and 5 (if appropriate). Other safety assessments include vital signs (blood pressure, pulse), urine pregnancy tests, and collection of adverse event data.

---

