**Investigational Product, Dose and Mode of Administration:**

---

DFD-01 (betamethasone dipropionate) Spray, 0.05%

The investigational product will be applied topically to all affected areas (i.e., those areas that were affected at Baseline, even if resolved, and new lesions that develop at any time during the treatment period) twice daily, approximately 12 hours apart. The target dose is at least 3 to 5 g per day (10 to 15 pumps, twice daily). Product is not to be applied to face, scalp, groin, axillae, or other intertriginous areas.

---

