### **5.2 Inclusion Criteria**

1. Subject and legal guardian understand the study procedures and agree to participate by giving assent and written informed consent, respectively. Legal guardian must be willing to authorize use and disclosure of protected health information collected for the study.
2. Subjects must be at least 12 years of age and no more than 16.9 years of age at the time of randomization.
3. Subjects must weigh at least 55 pounds at the Screening Visit.
4. Subjects must present with a clinical diagnosis of stable (at least 3 months) plaque-type psoriasis.
5. Subjects with psoriasis involving  $\geq$  10% BSA affected, not including the face, scalp, groin, axillae and other intertriginous areas.
6. Subjects must have an IGA grade of at least 3 (moderate) at the Baseline Visit.
7. All females must complete a urine pregnancy test (test must have a sensitivity of at least 25 mIU/mL for human chorionic gonadotropin) at the Baseline Visit (Visit 2), and the test result must be negative to be eligible for randomization.
8. Female subjects who are sexually active must agree to use contraception during the study. Reliable methods of contraception are:

- hormonal methods or intrauterine device in use  $\geq$  90 days prior to study product administration; or
- barrier methods plus spermicide in use at least 14 days prior to study product administration.
- partner has had a vasectomy at least 3 months previous to study product administration.

**Note:** Sexually inactive female subjects should be counseled to remain sexually inactive for the duration of the study and should be made to understand the possible risks involved in getting pregnant during the study. An abstinent female subject must agree that if she becomes sexually active during the study she will use an acceptable form of contraception.

9. Subjects must be in good general health as determined by the investigator and supported by the medical history and normal or not clinically significant abnormal vital signs (blood pressure and pulse).
10. Subjects whose results from the screening ACTH stimulation test are considered normal (blood cortisol level  $>18$  ug/dL at 30 minutes post stimulation) and show no other signs of abnormal HPA axis function or adrenal response.

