## **6.2 Treatment Regimen**

Subjects will use study product under the supervision and with help, if needed, of their legal guardian, twice daily with approximately 12 hours between applications for either 15 or 29 days starting on Day 1 during the study visit. Subjects will apply study product to all affected areas except the face, scalp, groin, axillae and other intertriginous areas. The target dose is at least 3 to 5 g per day (10 to 15 pumps of spray), twice daily, applied at approximately 2 mg/cm^2 on 10% BSA – 1500 cm^2). Subjects with greater than 10% BSA will apply more, as appropriate. All baseline affected areas and newly affected areas should be treated until the end of the study even if cleared. The investigator shall diagram the affected areas (in the source document), update the diagram at each visit, and remind the subjects and legal guardians where study product is to be applied at each visit using the diagram. Study product should be sprayed directly onto affected areas and rubbed in gently and completely. Study product should be applied after bathing, if applicable.

The first and last dates of treatment should be recorded in the CRF with the number of applications made on those days.

The first and last application of study product will be applied by the subjects or their legal guardian at the site under supervision. At the last visit, the bottle should be weighed before and after the application to determine the amount of study product applied for the last dose.

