## **6.3 Treatment and Protocol Compliance**

Subjects and legal guardians will be provided an instruction sheet specific for the study product, along with a diagram of affected areas to be treated. Study staff should review the instruction sheet and diagram with the subjects and their legal guardian to ensure protocol compliance. If new affected areas appear between visits, the subject may start treating the new area between visits. Treatment areas are to be updated on the diagram at each visit.

At each visit, the investigator or designee will interview subjects and their legal guardian concerning treatment compliance and ask if any doses have been missed. The investigator will also ask about compliance with protocol requirements. Protocol deviations will be recorded in the subject's chart and Protocol Deviation Form. A Protocol Deviation Form is not needed for

---

missed visits, missed applications, out-of-window visits and missing data. These items will be apparent from the missing data on the CRF and will be identified programmatically during data analysis for purposes of reporting. The sponsor should be consulted before discontinuing subjects due to protocol deviations unless safety is a concern.

Subjects/legal guardian will be provided a diary card for documenting the dates of applications. The subjects and legal guardian will review the diary card with the investigator or designee at each visit. The number of applications and the number of missed applications will be recorded on the CRF. By definition, there are no missed applications after the last date of treatment even if recorded on the diary.

In addition, bottles of study product will be weighed before dispensing and before and after the last application. These weights should be entered into the CRF.

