### 7.9.3 Visit 3 - Day 8 ± 3 days

1. Evaluate treatment and protocol compliance and record any deviations. This includes a review of the diary card for number of applications and missed applications.
2. Conduct clinical assessments:
  - a. IGA ([Table 2](#))
  - b. Local cutaneous safety evaluation for clinically significant atrophy and telangiectasia in the treated areas. The investigator should also ask the subject and legal guardian if any burning/stinging, pain, or itching has occurred in the treated areas since the last visit.
  - c. Update diagram of affected areas to be treated. Subjects should continue to treat areas that have cleared and any new areas that develop during the treatment period.
3. Collect vital signs (blood pressure, pulse).

4. Conduct urine pregnancy test for female subjects. Test must be negative to proceed.
5. Collect adverse event data. This includes a review of the diary card for potential AEs.
6. Update concomitant medications data.
7. Redispense diary and review instructions and diagram of affected areas to be treated with subject.
8. If subject requires more study product, weigh then dispense the assigned study product, as needed. Collect and record weight of empty or nearly empty bottles. Re-dispense partially filled bottles.
9. Schedule next visit. Remind the subject to come to the next visit well hydrated.
10. Complete CRF.

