**APPENDIX 2**  
**Subject Instructions - Spray**

1. You have been given a bottle of study medication. **Shake well before using.** Spray study medication directly onto each of your psoriasis lesions as instructed by the study nurse. Refer to the diagram provided. Apply study medication to all areas shown on the body diagram even if clear. Also apply study medication to new areas that may appear between visits. Apply study medication in the morning and at bedtime, approximately 12 hours apart. You will need to use at least 15-20 sprays of study medication each time. You can use more if needed. Massage lightly after application until medication disappears. If bathing at the treatment time, apply medication after bathing.
2. The study medication is for external use only. The study medication should not be used on the scalp, face, underarms, or groin area. Also avoid contact with eyes and lips. The application areas must not be bandaged, covered, or wrapped.
3. Always wash hands before applying the study medication and thoroughly after applying.
4. Store medication at room temperature.
5. If you have any questions, please ask the study coordinator or nurse.
6. The study medication may cause some irritation or discomfort. Tell your doctor about any reactions. If the reaction becomes severe, stop using the study medication and call the doctor.
7. Write down the date and time (am or pm) when you apply the study medication in your study diary.
8. Do not let anyone else use the study medication. Keep the medication out of the reach of children and pets. Use of the study product should be done under the supervision of the legal guardian.
9. Return all containers in the box at every study visit.
10. Bring your study diary to every visit.
11. If you cannot make a scheduled visit, please contact the study office as soon as possible to re-schedule another date.
- 12. Do not use study medication on the morning of your last study visit.**
13. If you have to discontinue participation in the study for any reason, notify the study office immediately. A visit will be scheduled for a final examination of psoriasis and to collect the containers and your diary. This visit is important for your safety.

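### The dose figures that define maximal use do not agree across Section 6.2, the Synopsis and Appendix 2, and Section 11 plans no summary of grams against area treated.

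*Combined protocol and SAP*

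**What the plan says.** The Synopsis states: "The target dose is at least 3 to 5 g per day (10 to 15 pumps, twice daily". Section 6.2 repeats the grams and pumps, but there the words for twice daily stand outside the bracket, so they could attach to the grams as well. Section 6.2 then adds the rate of about 2 mg/cm² and the worked area: "on 10% BSA – 1500 cm 2 ). Subjects with greater than 10% BSA will apply more, as appropriate". It gives no grams, pumps or scale for any area above 10% BSA.

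The sheet that subjects take home (Appendix 2, item 1) has one number for everyone: "You will need to use at least 15-20 sprays of study medication each time. You can use more if needed". The same item says: "Spray study medication directly onto each of your psoriasis lesions as instructed by the study nurse".

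Entry requires psoriasis on at least "10% BSA affected, not including the face, scalp, groin, axillae and other intertriginous areas" (Section 5.2), with no upper limit. The Synopsis (Methods) asks for at least 10% "body surface area (BSA) treated to achieve maximal use exposure".

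On compliance, Section 6.3 says: "The number of applications and the number of missed applications will be recorded on the CRF". At Visit 3 the site is told: "Collect and record weight of empty or nearly empty bottles". The last dose is weighed before and after application. Section 11.5.1 summarises applications, total grams and last-dose grams. Section 11.3 summarises BSA as a baseline variable. Section 11 also announces a separate SAP before database lock.

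**The concern.** Both objectives are set under maximal use conditions, so the amount applied per unit of skin is part of what the trial claims to test. Three figures define that amount (grams, pumps and mg/cm²). As written, they support daily doses that differ by a factor of two, and the subject sheet gives a fourth figure that matches none of them. A site that wanted to scale the dose to a large area would need the basis of the rate and the grams per spray, and neither is stated.

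The primary safety variable is the proportion with an abnormal cortisol response in about 25 subjects per arm, summarised descriptively. A low proportion reassures only if the intended amount reached the treated skin. The adult study quoted in Section 1 found 5 of 24 abnormal at 15 days and 0 of 24 at 29 days. If a similar pattern appeared here, dose per area would be a natural first check, and the planned summaries would not show it.

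**Working it through.** **Inputs.** 3–5 g, 10–15 pumps, 2 mg/cm² and 1500 cm² for 10% BSA (Section 6.2); 15–20 sprays (Appendix 2). Grams per spray is not stated. I derive it by pairing 3 g with 10 pumps and 5 g with 15.

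**The plan's own figure.** 2 mg/cm² × 1500 cm² = 3.0 g, the lower end of 3–5 g. The implied body is 1500 / 0.10 = 15,000 cm².

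**Size of the ambiguity.** If 3–5 g is per day, each application is 1.5–2.5 g. If it is per application, the day's total is 6–10 g.

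**Everything per application.** Grams per spray = 3/10 = 0.300 to 5/15 = 0.333. The printed minimum is 15 × 0.300 = 4.5 g to 20 × 0.333 = 6.67 g per application.

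**Everything per day.** Grams per spray = 3/20 = 0.150 to 5/30 = 0.167. The minimum is 30–40 sprays a day, again 4.5–6.67 g, now set against a daily need. The ratios are identical:

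| BSA | Grams needed at 2 mg/cm² | 15 sprays (4.5 g) | 20 sprays (6.67 g) |
|---|---|---|---|
| 10% | 3.0 | 150% | 222% |
| 15% | 4.5 | 100% | 148% |
| 20% | 6.0 | 75% | 111% |
| 30% | 9.0 | 50% | 74% |

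**Break-even.** BSA% = grams / 0.002 / 15,000 × 100.
- 15 sprays: 4.5–5.0 g, 2250–2500 cm², 15.0–16.7%.
- 20 sprays: 6.0–6.67 g, 3000–3333 cm², 20.0–22.2%.

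At the 10–15 pumps of Section 6.2 the dose is 3–5 g and break-even is 10–16.7%.

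**Mixed reading.** With grams per day and 2 mg/cm² per application, 15 × 0.150 = 2.25 g (1125 cm², 7.5%) and 20 × 0.167 = 3.33 g (1667 cm², 11.1%). This breaks the identity 2 mg/cm² × 1500 cm² = 3 g, so I treat it as less likely, but the wording does not exclude it.

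**Sensitivity to body size (assumed; the plan collects weight but not height).** The 4.5–6.67 g minimum covers 2250–3333 cm²:
- 10,000 cm²: 22.5–33.3% BSA
- 12,000 cm²: 18.8–27.8%
- 18,000 cm²: 12.5–18.5%
- 20,000 cm²: 11.2–16.7%

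**Sensitivity to grams per spray.** Cross-pairing the figures on a matched basis gives 3/15 = 0.2 g (break-even 10.0–13.3%) and 5/10 = 0.5 g (25.0–33.3%). That spread is itself a reason to state the number.

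**The case against.** A reader might infer that subjects with large areas will be under-dosed and that suppression will be understated. The documents do not support that. The 15–20 sprays are a minimum, the sheet allows more, and a nurse gives instructions. Section 6.2 says that larger areas get more, and all mapped areas must be covered. Staff review the diagram at visits, and the first and last applications are supervised. A shortfall needs a subject to stop at the minimum despite all this. No BSA distribution is given, so its frequency cannot be estimated. The spray-count mismatch also runs upward: at 10% BSA the sheet asks for more than Section 6.2 does. The Synopsis ties maximal use to at least 10% BSA treated, which every eligible subject meets, and plasma levels are measured directly. Finally, grams per %BSA can be computed at any time from collected data, and the SAP could include it.

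All of that stands against a claim of under-dosing. It does not remove the inconsistency. Rate times mapped area is a usable rule only once the basis of the rate and the grams per spray are known. Coverage governs where product goes, not how thickly, and compliance is counted in applications. The bottle is weighed before the first supervised dose, but no weight after it is specified. Plasma levels show exposure, but a low level alone cannot separate low absorption from thin application.

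**Conclusion.** The dose figures are inconsistent as written and should be reconciled, because they define the condition under which both objectives are to be met. The basis is ambiguous by a factor of two, and the subject sheet gives 15–20 sprays where Section 6.2 and the Synopsis give 10–15.

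On the protocol's own 15,000 cm² body, with grams and rate on one basis and grams per spray derived as above, the printed minimum is ample at 10% BSA and ceases to secure 2 mg/cm² above about 15–22% BSA. That threshold rests on the derived spray weight, the matched basis and the body size. It describes what the minimum guarantees, not what subjects will apply. Section 11 as it stands would not show whether high-BSA subjects reached the rate. The separate SAP may add this and is not in the text reviewed.

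**What to change.** 1. In Section 6.2 and the Synopsis, state whether 3–5 g and 2 mg/cm² are per application or per day, and state the grams per spray. Make the spray count the same there and in Appendix 2.
2. In Section 11.5.1 and the SAP, add by treatment group a descriptive summary and listing of mean grams per application (total grams / number of applications) and last-dose grams, each per 1% Baseline BSA. Show 0.30 g per 1% BSA (0.002 g/cm² × 150 cm²) only as the reference for a 15,000 cm² body. If the rate proves to be per day, halve it to 0.15 g for a single application. Footnote that the reference scales with body size (0.20 g at 10,000 cm², 0.40 g at 20,000 cm²) and that newly treated areas raise the ratio. Baseline BSA is the better denominator, because BSA affected at End of Treatment would omit cleared areas still being treated. Flag subjects with unreturned bottles.

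A mandatory minimum of one spray per 1% BSA is tempting but should not be adopted, because it ignores body size. At 30% BSA, 30 sprays (9–10 g) give 3.0–3.3 mg/cm² on 10,000 cm² and only 1.5–1.67 mg/cm² on 20,000 cm². It would also impose a higher corticosteroid minimum on small adolescents before grams per spray is known. At most, the site could write in a subject-specific number from the reconciled rate and the mapped area.

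The cost is protocol wording, one stated product figure, and one table with a listing from data already collected. No visits, samples, measurements or subjects are added.

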## **6.3 Treatment and Protocol Compliance**

Subjects and legal guardians will be provided an instruction sheet specific for the study product, along with a diagram of affected areas to be treated. Study staff should review the instruction sheet and diagram with the subjects and their legal guardian to ensure protocol compliance. If new affected areas appear between visits, the subject may start treating the new area between visits. Treatment areas are to be updated on the diagram at each visit.

At each visit, the investigator or designee will interview subjects and their legal guardian concerning treatment compliance and ask if any doses have been missed. The investigator will also ask about compliance with protocol requirements. Protocol deviations will be recorded in the subject's chart and Protocol Deviation Form. A Protocol Deviation Form is not needed for

---

missed visits, missed applications, out-of-window visits and missing data. These items will be apparent from the missing data on the CRF and will be identified programmatically during data analysis for purposes of reporting. The sponsor should be consulted before discontinuing subjects due to protocol deviations unless safety is a concern.

Subjects/legal guardian will be provided a diary card for documenting the dates of applications. The subjects and legal guardian will review the diary card with the investigator or designee at each visit. The number of applications and the number of missed applications will be recorded on the CRF. By definition, there are no missed applications after the last date of treatment even if recorded on the diary.

In addition, bottles of study product will be weighed before dispensing and before and after the last application. These weights should be entered into the CRF.

#### **6.4 Method of Assigning Subjects to Treatment Groups**

Approximately 50 subjects will be assigned randomly to one of the two treatment groups in a 1:1 ratio (25 for DFD-01 spray 29-day and 25 for DFD-01 spray 15-day). A subject randomization schedule will be created stratified by site. The site randomization schedule will be provided to each site for reference during randomization and drug dispensing. The next available randomization number and associated treatment duration will be assigned to subjects eligible for randomization at the time of study product dispensing in sequential order (e.g. the first subject to be dispensed study product for the first time on any particular day will be assigned the next available randomization number and study duration). No randomization number is to be skipped. The date and time of randomization, the randomization number and the assigned study product should be entered on the CRF. The randomization schedule will be generated and maintained by a third party vendor.

The investigator shall ensure that study products are only used by subjects under the investigator's personal supervision or under the supervision of a sub-investigator responsible to the investigator and in accordance with the protocol.

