### **6.1.4 Dispensing and Return**

One bottle of study product will be dispensed to subjects at the Baseline Visit (Visit 2) by study staff. The weight of the bottles should be recorded before dispensing. Additional bottles will be dispensed as needed. Partially filled bottles can be redispensed back to the subject. The study product to be dispensed for each subject will be identified by referring to the site randomization schedule. The tear-off panel is to be affixed to the source document. Subject initials and subject number must be written on the box label. Study staff will then dispense and instruct subject and legal guardian on study product use.

---

Dispensing and return of study product must be documented on the Investigational Product Site Dispensing and Return Log.

Subjects must return the used bottles even if empty throughout the trial. At the end of the trial, all used and unused bottles must be returned to the clinic for eventual destruction by the sponsor or designee. Any dispensed bottles that are not returned to the clinic must be documented on the log.

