### **7.9.2 Visit 2 - Day 1 - Baseline Visit**

1. Update the medical history and concomitant medications. Any medical event (not related to a protocol intervention) that occurred since informed consent was signed should be recorded as medical history if still ongoing.
2. Collect adverse events. Any new medical event, need for new medication, or change in medication dosing caused by a protocol procedure performed at the Screening Visit should

be considered an adverse event except for worsening of psoriasis.

3. Confirm eligibility according to inclusion/exclusion criteria.
4. Conduct urine pregnancy test on female subjects. Record method of contraception, as applicable, on source only.
5. Collect vital signs (blood pressure, pulse).
6. Conduct clinical assessments:
  - a. IGA ([Table 2](#))
  - b. Local cutaneous safety evaluation for clinically significant atrophy and telangiectasia in areas to be treated. The investigator should also ask the subject if any burning/stinging, pain, or itching has occurred in the areas to be treated in the last 14 days.
  - c. Diagram affected areas to be treated (excluding face, scalp, axillae, groin and other intertriginous areas).
  - d. Determine BSA excluding face, scalp, axillae, groin and other intertriginous areas.
7. Randomize the subject by referring to the randomization schedule and dispense study product to the subject/legal guardian. The tear-off panel from the box is to be affixed to the source document. Make a note on source document regarding treatment duration.
8. Instruct subject and legal guardian on study product use. Review the appropriate Subject Instructions with subject (See [Appendix 2](#)). Using the diagram of affected areas, have the subject treat the affected areas under supervision after weighing the study product.
9. Dispense and review use of diary. Remind subject and legal guardian to record actual application dates and/or potential adverse events as well as any medication used in the diary and to bring diary to each visit.
10. Schedule next visit.
11. Complete CRF for all subjects including screen failures. Only enter concurrent medical conditions and concomitant medications on the CRF.

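### Allocation is not concealed: each site is given the schedule that pairs randomization numbers with treatment durations, so staff could know the next duration before booking Baseline or scoring IGA and BSA

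*Combined protocol and SAP*

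**What the plan says.** Section 6.4 describes a 1:1 allocation of about 50 subjects, stratified by site. On who makes the list: "The randomization schedule will be generated and maintained by a third party vendor". On who uses it: "The site randomization schedule will be provided to each site for reference during randomization and drug dispensing". On how it is used: "The next available randomization number and associated treatment duration will be assigned to subjects eligible for randomization at the time of study product dispensing". Numbers are taken in sequence and none may be skipped.

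Two other sections agree. Section 6.1.4: "The study product to be dispensed for each subject will be identified by referring to the site randomization schedule". Section 7.9.2, step 7: "Randomize the subject by referring to the randomization schedule and dispense study product to the subject/legal guardian".

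Eligibility is settled at the same visit. Step 3 reads "Confirm eligibility according to inclusion/exclusion criteria" and step 6d reads "Determine BSA excluding face, scalp, axillae, groin and other intertriginous areas"; IGA is step 6a. Section 5.2 sets the thresholds: "Subjects must have an IGA grade of at least 3 (moderate) at the Baseline Visit", and at least 10% BSA, which section 7.3 has estimated by hand print. Section 7.2 lets Baseline fall 14 to 28 days after the screening ACTH test.

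No section mentions envelopes, central or interactive release, masking of the list, or who at the site may see it.

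**The concern.** Concealment before assignment is a separate matter from blinding after it. An open-label trial can have full concealment, so sections 6.5.1 and 6.5.2 do not settle the point.

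A readable site list leaves two routes for selection. Staff could decide which waiting subject comes to Baseline next, using the two-week booking range. They could also let the coming duration influence a borderline IGA or hand-print BSA. Good general health (inclusion 9) and inability to comply (exclusion 11) are further judgements. Expected compliance is relevant because the 29-day arm has one more scheduled visit and two more weeks of twice-daily application. ACTH eligibility is a laboratory cutoff and leaves little room for judgement.

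At stake is the comparability of the two durations. Section 11.5.3 reports the suppression proportion by treatment group. Section 1 reports 5 of 24 (20.8%) suppressed at 15 days and 0 of 24 at 29 days in adults, so readers will compare the arms whether or not a test is planned. Selection could move either arm's figure.

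**Working it through.** **Plan's own figure.** 25 + 25 = 50, as section 11.1 says. That section gives no statistical justification for the size and no test is planned, so there is no power calculation to reproduce.

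**What each safeguard does**

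| Safeguard | Section | Hides the next duration? |
|---|---|---|
| Vendor generates and maintains the list | 6.4 | No; the site still receives it |
| Sequential use, no skipping, eligible subjects only | 6.4 | No; fixes the order of numbers, not which subject meets the next one |
| Randomization at step 7, after IGA and BSA | 7.9.2 | No; the list can be read earlier |
| Date and time of randomization on the CRF; screen-failure reasons; log | 6.4, 7.2, 9.3 | No; allows audit afterwards |

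**Size: an illustration.** Every input here is assumed; none is in the documents. A two-level factor is held by a share p of subjects. Suppression is 30% with it and 10% without, with no effect of duration. At a share s of slots, staff choose between two candidates, and all sites steer the same way.

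- Factor share, favoured arm: (1 − s)p + s[1 − (1 − p)²]
- Factor share, other arm: (1 − s)p + s·p²
- Difference: 2sp(1 − p)
- Gap in suppression: (30 − 10) points × difference
- Standard error of the suppression difference at 20% and 25 per arm: √(2 × 0.2 × 0.8 / 25) = 11.3 points
- Standard error of the factor-share difference: √(2 × 0.5 × 0.5 / 25) = 14.1 points
- Expected cases moved per arm: 25 × gap / 2 (one subject is 4 points)

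| p = 0.5 | s = 0.25 | s = 0.5 | s = 0.8 |
|---|---|---|---|
| Factor share by arm | 56.25% vs 43.75% | 62.5% vs 37.5% | 70% vs 30% |
| Difference in share (multiple of 14.1) | 12.5 points (0.9) | 25 points (1.8) | 40 points (2.8) |
| Suppression by arm | 21.25% vs 18.75% | 22.5% vs 17.5% | 24% vs 16% |
| Gap (multiple of 11.3) | 2.5 points (0.22) | 5 points (0.44) | 8 points (0.71) |
| Cases moved per arm | 0.3 | 0.6 | 1.0 |

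**Sensitivity.** With p = 0.3 or 0.7 the gaps are 2.1, 4.2 and 6.7 points. If k of 8 equal sites steer one way and the rest the other, the gap is multiplied by (2k − 8)/8: at k = 6 it halves to 1.25, 2.5 and 4 points, and at k = 4 it is zero. Sites average 50/8 = 6.25 subjects, so a choice at half or more of the slots is doubtful.

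**Visibility.** Section 11.3 tabulates baseline characteristics by group. A tabulated factor such as BSA would stand out only in the larger cases; an unrecorded factor would not show in any.

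**Predictability.** With a readable list the next duration is known. With concealment, the correct-guess rate is 50% under unrestricted allocation. For known blocks of size 2m it is [m + 0.5(4^m / C(2m, m) − 1)] / 2m, which gives 75%, 71% and 68% for blocks of 2, 4 and 6. Block size is not stated.

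**The case against.** The case for leaving this alone, or for only asking for clarification, has several parts.

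- **Little depends on the contrast.** The objectives are per duration, no inferential testing is planned, and the endpoint is a laboratory cutoff. This stands, and is why the effect is called modest.
- **The form of the list is not stated.** A masked list would fit some of the wording. This also stands: foreknowledge is possible, not shown. But three sections consistently describe a list consulted at the site, so even on that reading the text needs a sentence.
- **Other checks exist.** IGA and BSA are also recorded on source at Screening (7.9.1, steps 7 and 8), subjects should tentatively qualify before the ACTH test (7.2), monitors visit several times (10), and weight, sex, race, ethnicity and the baseline ACTH result are also baseline characteristics (7.3). These make a shifted Baseline score easier to detect later. They do not hide the next entry or address the order of booking.
- **The illustration is assumed and partial.** It models the choice between candidates, not the scoring route, and nothing in the documents suggests a common direction of steering; the adult results do not suggest an obvious one. This stands.
- **Concealment would not remove everything.** If small blocks are used and staff can infer their size, a guess rate g leaves roughly 2g − 1 of the steering: 2 × 0.75 − 1 = 50% for blocks of 2, and 2 × 0.683 − 1 = 37% for blocks of 6. The 2.5-point case would then improve by about 1.25 to 1.6 points. This is fair, and is a reason not to disclose any block size.

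**Conclusion.** The concern holds. The protocol gives sites the list, has them randomize and dispense from it, and describes nothing that hides the next duration before eligibility is settled. The safeguards present fix the order of use and permit audit; they do not conceal.

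The likely size is small. Under the assumed inputs, the most plausible of the three cases is a 2.5-point spurious gap, about 0.3 of a case per arm and 0.22 of a standard error, and it still needs every site to steer the same way. No selection has been shown. The change is worth making because it is standard and nearly free and protects the comparability that randomization is meant to provide, not because a large bias is expected.

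**What to change.** - **Section 6.4.** Delete the sentence that gives sites the schedule. State that the vendor already named holds the list and releases one assignment (number and duration) at a time, by phone, email or web, or by site-specific, sequentially numbered, opaque sealed envelopes. Release follows only once all Baseline eligibility items, including pregnancy test, vital signs, IGA and BSA, are recorded, that is, after step 6 of section 7.9.2. Any block size is not disclosed to sites.
- **Section 6.1.4.** Have product and duration identified by the released assignment instead of the site list.
- **Section 7.9.2, step 7.** Have staff obtain the next assignment after eligibility, including steps 3 to 6, is recorded.
- **If the list is already masked,** say so in section 6.4 and state who may reveal an entry and when.

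Both arms use the same product, so dispensing does not require sites to hold the list.

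Cost: a small release step by the existing vendor, or up to 8 × 15 = 120 envelopes (site maximum from section 5.1, because the schedule is stratified by site); three text edits; possibly a short wait at Visit 2. No added subjects, visits or analyses.
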